Aneurysm Dome		Maximum horizontal diameter of the aneurysm.	
Aneurysm Neck		Opening of the aneurysm where it meets the parent vessel	
Aneurysm Occlusion		 According to the Raymond–Roy Scale¹: Class 1: Complete Occlusion – complete obliteration of the aneurysm. Class 2: Residual Neck – persistence of any portion of the original defect of the arterial wall as seen on any single projection, but without opacification of the aneurysmal sac. Class 3: Residual Aneurysm– any opacification of the aneurysmal sac. 	
Attempted Procedure		Any procedure where Pipeline [™] Vantage Embolization Device with Shield Technology [™] was attempted i.e., successful puncture at the arterial access site.	
Bleeding Complications per GUSTO		 Bleeding complications shall be adjudicated using the GUSTO bleeding criteria which includes categorizing all bleeding events into the following categories: Severe or Life-threatening: Intracerebral hemorrhage Resulting in substantial hemodynamic compromise requiring treatment Moderate: Requiring blood transfusion but not resulting in hemodynamic compromise Mild Bleeding that does not meet above criteria 	
Cerebral Infarction		Evidence of new ischemic changes (infarction) on imaging. Further characterized as:	

PR-NV16099	Version C	Page 13 of 144 Mectronic
		 Asymptomatic: no associated focal neurological deficit symptoms (i.e., Silent Infarctions) Symptomatic: focal neurological deficit
Contrast Induced Complications		symptoms lasting less than 24 hours Complications arising due to the use of contrast agent used for imaging requirements during study procedure(s).
Delayed Intra-Cranial Hemorrhage (IC	н)	Any intracranial hemorrhage occurring >30 days post- procedure
Device Deficiency (DD)		Inadequacy of a medical device with respect to its identity, quality, durability, reliability, safety or performance. (ISO 14155:2011 3.15) Note: Device deficiencies include malfunctions, use errors, and inadequate labeling.
Device Movement		Unintended Pipeline stent (braid) Movement (as observed/discerned on imaging) of the implanted device following deployment.
		Device movement will be further characterized by:
		 Timing: Intra-procedural: Observed during the study index procedure
		 Post-procedural: Observed at a follow-up time point
		 Foreshortening: Movement on either or both ends of the device in opposite direction towards the aneurysm neck.
		 Migration: Movement of device where both ends move in a single direction away from the aneurysm neck.

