		• Device Embolization into Aneurysm: Herniation into the aneurysm

PR-NV16099	Version C	Page 14 of 144		Medtronic
		linical Significance.		
		 Inical Significance: Clinically Significant: W causes unintended openin leading to incomplete occ retreatment of the aneury Not Clinically Signific movement does not cause the aneurysm neck le occlusion nor is a reason aneurysm. 	g of the ar lusion or i /sm. a nt: W e unintend rading to	neurysm neck s a reason for hen device ed opening of incomplete
Device Technical Success	s	vevice level analysis providing tudy device implantations at ptal number of devices attemp	he target	site with the
Device Thrombosis	tł E	 ost-procedural, de novo formative normality within the device visionach Device Thrombosis event with reference to symptoms reference to symptoms reference to symptom presumed to be relaced to be relaced to be related to be related	ualized on i will also ported for coms repo ated to s reporte	maging. be reported the subject: rted that are the device d that are
Dome-to-Neck Ratio	A	neurysm dome max diameter,	aneurysm	neck width
Enrollment		ointat which the subjectsigns nformed Consent.	the study	authorized
Excessive Radiation Complications	р	ny noted procedural complica resumed to result from excess ue to imaging modalities.		
Index Procedure	d	he first intended procedure to evice where a successful punc ccess site is completed.	-	
Institutional Review Board/Research		nstitutional Review Board (IRB) onstituted group that has beer		

PR-NV16099	Version C	Page 15 of 144 Medtronic	
		to review and monitor biomedical research involving human subjects.	
		The Research Ethics Board (REB) helps ensure that this research meets the highest ethical standards, and that the greatest protection is provided to participants who serve as research subjects.	
Intention to Treat Population (ITT)		All subjects who were consented and in whom deployment of the Pipeline [™] Vantage Embolization Device with Shield Technology [™] was attempted (successful puncture at the arterial access site), independent of the procedure being completed successfully.	
Intra-Cranial Hemorrhage		Intra-Cranial Hemorrhage:	
		Hemorrhage within the fixed vault of the cranium (skull). ICH will be further categorized as:	
		 Intracerebral Hemorrhage: 	
		 Intra-Parenchymal Hemorrhage (IPH): 	
		• Bleeding within the cerebral matter (brain parenchyma), not involving the ventricles.	

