4.2.4. ASPIRe: Aneurysm Study of Pipeline[™] in an Observational Registry

ASPIRe was a prospective, multi-center, single-arm, post-market registry of 191 intracranial aneurysm patients with 207 aneurysms from 28 worldwide centers who underwent PED treatment. The 207 aneurysms in the study had a median follow-up duration of 6.6 months. The majority of aneurysms treated were saccular and overall average size of treated aneurysms was 14.5 mm.

Neurological morbidity was 6.8% (13/191) and the neurologic mortality rate was 1.6% (3/191). The combined rate of neurological morbidity and mortality was 6.8% (13/19), with the most common major adverse event of interest being intracerebral hemorrhage (3.7%, 7/191) followed by ischemic stroke (1.6%, 3/191). Most of the major adverse events (6.3%, 12/191) occurred in the early post-operative phase within the first 30 days following PED treatment.

Aneurysm occlusion was assessed by an independent core lab according to the Scale of Roy at last visit for all subjects with imaging follow-up of at least 6 months. The median follow-up duration was 7.8 months and complete occlusion was reported in 75% of subjects (77/103).

The ASPIRe registry, as a comprehensive evaluation of PED use in the real world, confirmed that the PED is safe when used for the treatment of intracranial aneurysms in routine clinical practice, reporting a 6.8% rate of associated major morbidity and neurological mortality.

4.2.5. PREMIER: Prospective Study on Embolization of Intracranial Aneurysms with the Pipeline[™] Device

PREMIER was the first prospective, multicenter trial to evaluate the use of the Pipeline[™] device for the treatment of small and medium, unruptured aneurysms of the intracranial carotid and proximal vertebral artery. The study was conducted in 1 Canadian and 22 US centers.

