ADVANCE Clinical Investigation Plan Medtronic PR-NV16099 Version C Page 41 of 144 Medtronic

Occurrence of major stroke in the territory supplied by the treated artery or neurological death at 1-year post-procedure (primary safety endpoint) occurred in 3.23% of subjects. Major stroke in the territory supplied by the treated artery or neurological death at 30 days post-procedure due to procedural complications were observed in 2.9% (6/204) of subjects. No delayed intracerebral hemorrhage (>30 days to 1-year post-procedure) was observed (0.0%). Overall, the incidence of major stroke, neurological death, and delayed intracerebral hemorrhage in the SHIELD study was low. Through the 1-year follow-up, the rate for death was 1.0% (2/204) (same for neurological death), all stroke was 6.4% (13/204), disabling stroke as observed (including death) was 1.0% (2/200), and ICH was 4.4% (9/204). Summary of primary endpoints of SHIELD study is presented in **Table 4-1**.

Endpoints	Rates	2-sided 95% exact binomial confidence interval				
Primary Effectiveness Endpoint: Complete aneurysm ocdusion (defined as Raymond-Romparent artery stenosis (≤ 50%) or retreatment of the target a neurysm at 1-year post-proc		ut significant				
FAS# population (N=200)	71.67%	(64.95%,77.74%)				
ICA ⁺ -FAS population (N=149)	75.30%	(67.58%,81.99%)				
Primary Safety Endpoint : Occurrence of major stroke in the territory supplied by the treat 1-year post-procedure	ated artery or neu	rological death a t				
ITT* population (N=204)	3.23%	(1.27%,6.68%)				
ICA [†] population (N=153)	3.27%	(1.07%,7.46%)				
*Intention to Treat (ITT) population includes all consented subjects in whom deployment of the Pipeline [™] Shield device was attempted. For the ITT population, primary effectiveness endpoint analysis was based on Full Analysis Set (FAS) population and safety analysis was based on the ITT population. #Full Analysis Set (FAS) is defined as a subset of the ITT population including only those in whom the Pipeline [™] Shield device was implanted.						
†Internal Carotid Artery population (ICA population) is defined as a subset of ITT population that inclu Pipeline™ Shield device was implanted in the ICA (segments C2-C7). For the ICA population, primary based on FAS (referred to as ICA-FAS) and safety analysis was based on the ICA population.	•	•				

Table 4-1. Summary of Primary Endpoints of SHIELD Study

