5.1.2.1. Secondary Endpoint(s)

The following will be assessed for the effectiveness outcome measures:

- 1. Incidence of successful device implantation at the target site
- 2. Incidence of complete aneurysm occlusion (Raymond Roy Class 1) at 1- and 3-years postprocedure
- 3. Incidence of target aneurysm recurrence at 1- and 3-years post-procedure

For the purposes of this study protocol, successful device implantation will be presented in terms of Procedural Technical Success and Device Technical Success. Procedure technical success is measured by the rate of successful implantation of the study device during the study index procedure at the target site regardless of the number of devices deployed and implanted at the target site. Device technical success is measured by the rate of successful study device implantation at the target site with the total number of devices attempted to be deployed.

Successful device implantation and retreatment will be site reported. Aneurysm occlusion class, recurrence, and parent artery stenosis will be assessed by the independent Imaging Core Lab.

The following will be assessed for the secondary safety endpoints:

- 1. Incidence of major stroke in the territory supplied by the treated artery or neurological death at 2- and 3-years post-procedure
- 2. Incidence of major stroke in the territory supplied by the treated artery or neurological death at 30 days post-procedure
- Incidence of delayed intraparenchymal hemorrhage >30 days post-procedure through 1-year post-procedure
- Incidence of subjects with disabling strokes that have a mRS decline to a score of 3 or more (mRS ≥ 3) due to a stroke-related cause assessed at a minimum of 90 days post-stroke event at 1 year, 2 year, and 3 year post-procedure

The events comprising the safety endpoints will be adjudicated by the independent CEC.

PR-NV16099

Version C

Page 47 of 144

6. Study Design

The study is a prospective, global, multi-center, single-arm IDE clinical study evaluating the performance of the Pipeline[™] Vantage Device. The Pipeline[™] Vantage Device is investigational in the United States and Canada.

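### The plan gives a hemorrhage rate only for parenchymal bleeds from day 31 to 1 year; some early intracranial bleeds enter no endpoint, and the others are merged with ischemic events

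*Combined protocol and SAP*

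**What the plan says.** Among the secondary safety endpoints in Section 5.1.2.1, repeated in Section 13.8.3, the only one named for hemorrhage is "Incidence of delayed intraparenchymal hemorrhage >30 days post-procedure through 1-year post-procedure". The glossary (Section 2) defines intraparenchymal hemorrhage as "Bleeding within the cerebral matter (brain parenchyma), not involving the ventricles" and lists ventricular, subarachnoid, subdural and epidural bleeding as separate kinds of intracranial hemorrhage (ICH). The glossary entry for delayed ICH is wider than the endpoint: "Any intracranial hemorrhage occurring >30 days post- procedure".

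Three other endpoints can pick up a bleed:

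- The primary safety endpoint counts major stroke (NIHSS rise of 4 or more) in the treated territory, or neurological death, to 1 year. Section 5.1.1.1.2 counts hemorrhagic presentations as stroke.
- The same composite is a secondary endpoint at 30 days and at 2 and 3 years.
- Disabling stroke (mRS of 3 or more) is assessed at 1, 2 and 3 years, with no NIHSS cut.

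ICH is also an event of interest (Section 10.1) that the clinical events committee (CEC) adjudicates (Section 12.1). Section 13.8.4 groups adverse events by relatedness, seriousness and severity, at 1 year, 1-2 years and 2-3 years. Apart from unanticipated device effects, its groups take only events rated causal or probable. Section 13.8.3 makes all secondary endpoints descriptive.

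**The concern.** Section 10.4 names intracranial hemorrhage among the main potential risks, with published rates of 0.6% to 12%, and offers dual antiplatelet therapy as one possible cause. Section 9.6 keeps both antiplatelet agents going for at least 3 months, so the first 30 days fall within that treatment. Yet the endpoint skips those days, every non-parenchymal bleed, and everything after 1 year.

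The adverse event tables do not fill the gap. They name no hemorrhage row and have no early band. They also omit events rated possible, which is where Section 11.1.8 places cases whose relatedness cannot be assessed. An early bleed of unclear cause could therefore be adjudicated and still appear in no planned table. If predecessor experience is a guide, the one hemorrhage rate that the study reports will be close to zero and could be read as the bleeding risk of the device.

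**Working it through.** **Predecessor figures, reproduced**

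| Study (section) | Count | Rate |
|---|---|---|
| SHIELD (4.2.7), ICH to 1 year | 9/204 | 4.41% (exact 95% CI 2.04 to 8.21) |
| SHIELD (4.2.7), intracerebral, day 31 to 1 year | none observed | 0.0% |
| ASPIRe (4.2.4), intracerebral | 7/191 | 3.66% |
| ASPIRe (4.2.4), major events within 30 days | 12/191 | 6.28% |
| PREMIER (4.2.5), intracerebral, day 31 to 1 year | denominator not given | 0.73% |
| PFLEX (4.2.8), intracerebral, day 31 to 1 year | 0/50 | 0.0% |

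All agree with the rounded values in the protocol. PREMIER's 0.73% fits 1/137 = 0.730%, which is assumed below.

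**Expected yield of the planned endpoint, n = 100**

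The chance of no event is (1 - p)^100.

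- PREMIER alone, p = 0.0073: expected 0.73 events; P(0) = 0.9927^100 = 48%.
- Pooled, p = 1/(137 + 204 + 50) = 1/391 = 0.26% (exact 95% CI 0.01 to 1.42): expected 0.26 events; P(0) = 77%; P(at most 1) = 97%.

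The pooled rate also assumes that SHIELD's zero refers to all 204 subjects. With only the 171 who returned at 1 year, p = 1/358 = 0.28% and P(0) = 76%.

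The predecessors report intracerebral hemorrhage, which in this glossary includes ventricular bleeding. The planned endpoint is narrower, so these rates are more likely too high than too low.

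**Bleeding without the window, n = 100**

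- SHIELD's rate, all ICH: expected 4.4; P(0) = (1 - 9/204)^100 = 1.1%.
- ASPIRe's rate, intracerebral: expected 3.7; P(0) = (1 - 7/191)^100 = 2.4%.

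The gap between the two blocks reflects bleed type as well as time window, so it does not measure the effect of the window alone.

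**What can be said about timing**

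ASPIRe states: "Most of the major adverse events (6.3%, 12/191) occurred in the early post-operative phase within the first 30 days following PED treatment". It had 13 subjects with neurological morbidity or mortality. If all 7 hemorrhages occurred among those 13, and 12 of the 13 had early events, at most one hemorrhage was late and at least 6 of 7 were early. This is an inference: the 12 are major events of all kinds, and median follow-up was only 6.6 months.

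**Whether the composites absorb the bleeds**

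For SHIELD, 30-day major territory stroke or neurological death is given as events "due to procedural complications were observed in 2.9% (6/204) of subjects". With ICH counted per subject, at least 9 - 6 = 3 ICH subjects lay outside that count. Against the 1-year composite, 3.23% of 204 is 6.6 subjects, so at most 7, which leaves at least 9 - 7 = 2 outside. SHIELD also had 2 disabling strokes (2/200, deaths included). If both were separate from the composite and both were bleeds, the lower bound falls to 0.

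**The case against.** The other side has four good points.

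1. **Early bleeds are not ignored.** The primary safety endpoint runs from day 0 and counts hemorrhagic stroke, a 30-day composite covers the early window, and the disabling-stroke endpoint takes early bleeds whatever the NIHSS change. A reader might infer that every early bleed with an NIHSS rise below 4 is lost. The documents do not support that: fatal and disabling ones count.
2. **The predecessor studies do not agree.** A reader might infer that all of them place bleeding in the first 30 days. PREMIER had 0.73% delayed hemorrhage and no major territory stroke or neurological death at 30 days from procedural complications, although that is not a count of early bleeds. PFLEX gives no early hemorrhage count. SHIELD sets all ICH against delayed intracerebral hemorrhage; some of its 9 could be late bleeds of another type. Nor do its counts prove that any bleed would have escaped every endpoint.
3. **The window has a purpose.** PREMIER, SHIELD and PFLEX all report hemorrhage after 30 days to 1 year, so the endpoint allows comparison. It is labelled as delayed, is not tested, and supports no success claim. A reader might infer that the headline safety result is understated; the headline is the primary composite, which this does not touch.
4. **The data will exist.** ICH is collected and adjudicated, the 1-year table covers days 0-30 for related events, and Section 13.1 promises a fuller SAP.

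All four stand. They narrow the point without removing it: no section names an incidence for early or non-parenchymal intracranial hemorrhage, and the planned tables filter on relatedness.

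**Conclusion.** The concern holds as a gap in planned reporting, not in data collection or in the primary analysis. Non-fatal, non-disabling bleeds in the first 30 days that are not major treated-territory strokes enter no endpoint. Other early bleeds are merged with ischemic events.

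The one hemorrhage rate that is planned will probably rest on zero or one event: no event in about 48% of trials at PREMIER's rate, and about 77% at the pooled rate. These figures assume that predecessor rates carry over to this device and population, a PREMIER denominator near 137, and full SHIELD follow-up. SHIELD and, by inference, ASPIRe suggest that much of the bleeding lies outside the window, but its early timing is suggested rather than proven. The case for a change does not depend on that timing, because the plan lacks the rate either way.

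**What to change.** Keep the delayed endpoint for comparison with the predecessor studies. In Sections 5.1.2.1 and 13.8.3, add descriptive rows for CEC-adjudicated intraparenchymal hemorrhage and for all intracranial hemorrhage, regardless of relatedness, with exact 95% intervals, for:

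- day 0-30;
- day 31 to 1 year;
- cumulative to 1 year;
- cumulative to 3 years.

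Present the delayed rate beside the cumulative rate.

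The cost is a few table rows from events already collected and adjudicated. No alpha, sample size, visit, reader or clinical rule changes. The drawback for the sponsor is a less favourable reported bleeding rate.

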6.1. Duration

Subjects will actively participate for approximately 3 years. Study participation includes Baseline, Pre-Procedure, Post-Procedure, Discharge exam, and follow-up visits at 30-day, 180-day, 1-year, 2-year and 3-year. Enrollment will be approximately 1 year. The total study duration is expected to be approximately 4 years.

6.2. Rationale

The Pipeline[™] Embolization Device has been commercialized in the US since 2011 for the endovascular treatment of adults with large (≥ 10-24 mm) or giant (≥ 25 mm) wide-necked intracranial aneurysms in the ICA from the petrous to the superior hypophyseal segments. Over time, additional long-term data has been generated which further confirms the safety and effectiveness of the Pipeline[™] Embolization Device for this indication. Additionally, outside the US, the Pipeline[™] Embolization Device has been approved and commercialized since 2008 for endovascular embolization of cerebral aneurysms.

The latest developmental modification to the Pipeline[™] Embolization Device (PED) system is Pipeline[™] Vantage Embolization Device with Shield Technology[™]. Pipeline[™] Vantage utilizes the same phosphorylcholine (PC) surface treatment (Shield Technology[™]) as the Pipeline[™] Flex Embolization Device with Shield Technology[™]. Additionally, the wire design and braid pattern are unchanged in Pipeline[™] Vantage. However, there are some key enhancements in the Pipeline[™] Vantage device. Pipeline[™] Vantage implant has larger implant diameters and longer lengths, drawn filled tubes and decreased wire diameter as well as increased pore density (Section 7.1.1). These changes to the implant increase radiopacity, optimize deliverability and enhance the ability of the implant to open upon deployment. The Pipeline[™] Vantage delivery system (Section 7.1.1.4) was designed to be compatible with 0.021" inner diameter micro catheters for select sizes and also includes a new Advanced Resheathing Mechanism, Corewire-based Delivery System and Corewire Subassembly for improved reliability. The Shield Technology™ surface treatment applied to the implant is an inert, PC polymer material that is chemically bonded to the braid surface. The polymer is a chemically derived material, created to mimic the outer membrane of a human red blood cell. Shield Technology™ reduces the material thrombogenicity of the braid surface compared to the current bare metal Pipeline™ Embolization Device implant based on bench data with human platelets and plasma.

Objective evidence on the safety and effectiveness of the Pipeline[™] Vantage Device is best collected by conducting a prospective study with standardized follow-up evaluations. The use of an independent core

Medtronic Controlled Information

Ρ

ADVANCE	Clinical Investigation Plan		
PR-NV16099	Version C Page 48 of 14	4	Medtronic

lab is uncommon in studies evaluating intracranial aneurysms despite evidence showing site reported data underestimates unfavorable angiographic appearance.^{97,98} Along with an independent core lab, the Pipeline[™] Vantage Device trial will employ an independent Data Monitoring Committee (DMC) and an independent Clinical Events Committee (CEC) to assist in the oversight and analysis of the study data. Treatment with the Pipeline[™] Vantage Device is expected to show high complete aneurysm occlusion rates and minimal safety events.

The patient population proposed for enrollment in the study includes patients with a wide-neck intracranial aneurysm located in the internal carotid artery (up to the carotid terminus). The justification for the patient population and the single-arm study design is provided below.

Small, Medium, Large, and Giant Wide-Necked Aneurysms

Pipeline[™] Flex Embolization Device flow diverter is currently indicated in the US for the endovascular treatment of adults (22 years of age or older) with large or giant wide-necked intracranial aneurysms (IAs) in the internal carotid artery from the petrous to the superior hypophyseal segments. The Pipeline™ Flex embolization device is also indicated for use in the internal carotid artery up to the terminus for the endovascular treatment of adults (22 years of age or older) with small and medium widenecked (neck width \geq 4 mm or dome-to-neck ratio < 2) saccular or fusiform intracranial aneurysm (IAs) arising from a parent vessel with a diameter \ge 2.0 mm and \le 5.0 mm. The device has shown high effectiveness and low complication rates for this indication.⁸⁴

In addition to evaluating large and giant wide-neck aneurysms, the proposed study also aims to include wide-neck aneurysms measuring <10mm. There is a lack of consensus in the literature and guidelines on whether small and medium size aneurysms should be treated. The natural course of untreated aneurysms of specific size ranges has not been clearly identified.⁹⁹⁻¹⁰³ Although several studies have reported a wide range of rupture rates over time for untreated small and medium size aneurysms of various locations; annual rupture rates for small and medium size aneurysms vary significantly up to a 20 fold difference (0.05% vs. 1.0%, annually).^{99,102-106} This most likely can be explained by the fact that in addition to aneurysm size, the risk of aneurysm rupture is attributed to various other factors, including aneurysm morphology, location, previous subarachnoid hemorrhage, and subject characteristics.^{100,105,107,108}

In the Small Unruptured Intracranial Aneurysm Verification (SUAVe) Study, patient age, aneurysm diameter \geq 4 mm, hypertension, and aneurysm multiplicity were significant predictive factors for rupture of small aneurysms.¹⁰⁸ The average annual risk of rupture for small aneurysms (<5 mm) in the study was 0.54% overall, 0.34% for single aneurysms and 0.95% for multiple aneurysms (mean follow-up: 41 months).¹⁰⁸ Another study which followed the natural course of unruptured aneurysms with a mean size of 5.7 mm in 5720 patients reported a similar annual rupture rate to the SUAVe study at 0.95% (followup: 3 months to 8 years). The annual rupture rates from both studies, however, may be an underestimate

ADVANCE Clinical Investigation Plan Image: Clinical State of the state of th

due to possible selection bias. Data from patients who underwent surgical intervention were censored and some of these patients may have been at an increased risk for rupture.^{100,108}

Although the rupture rate for untreated unruptured small and medium aneurysms is low, it is also important to consider that the majority of unruptured intracranial aneurysms are small and medium in size. In the International Study of Unruptured Intracranial Aneurysms (ISUIA) study, out of 1692 untreated, 1917 surgically treated, and 451 endovascularly treated subjects, 85%, 78%, and 58% of the subjects' aneurysms were ≤ 12 mm in size, respectively. In a meta-analysis of 71 studies investigating the endovascular treatment of intracranial unruptured aneurysms, of the 2688 patients included, 75% of the patient's aneurysms' were < 10 mm in size. Furthermore, in recent randomized controlled trials in which bare metal coils were studied against alternative treatment options in hundreds of patients, both unruptured and ruptured aneurysms were included and the majority of patients treated had small and medium size aneurysms.^{14,109-112}

Data for ruptured aneurysms also supports the treatment of small and medium aneurysms. Many of the aneurysms that rupture are small or medium in size. In the International Subarachnoid Aneurysm Trial (ISAT), a landmark trial on the treatment of 2143 ruptured intracranial aneurysms, 92% of the ruptured aneurysms were $\leq 10 \text{ mm.}^{27}$ Similarly, in the CLARITY study of ruptured aneurysms, 89.5% (700/782) of the subjects had an aneurysm $\leq 10 \text{ mm.}^{113}$ Treatment of a ruptured aneurysm is critical in order to stop the bleeding and attempt to reduce the risk of potentially devastating complications. Since a significant majority of ruptured aneurysms reported in the literature appear to be small and medium in size, these findings support the fact that these aneurysms pose a considerable risk and warrant careful consideration for treatment.^{26,27,101,114}

Multiple publications demonstrate that these small and medium wide-necked aneurysms are commonly treated endovascularly with SAC.¹¹⁵⁻¹²² Although initial occlusion rates are good, the primary limitation of SAC is the inability to provide sustained long-term aneurysm occlusion. Aneurysm recurrence rates of up to 16% have been reported in the literature after SAC treatment of small and medium IAs.^{30,115,117,118,121,123,124} The presence of major aneurysm recurrence requires retreatment, which is evidenced by aneurysm retreatment rates of up to 10% for small and medium IAs.^{119,121-126} Therefore, an alternative approach for obtaining sustained aneurysm occlusion, such as flow diversion, is needed for small and medium wide-necked intracranial aneurysms.

In the IntrePED trial, a post-market registry to evaluate the Pipeline[™] Embolization Device in which all consecutive subjects treated with the Pipeline[™] Embolization Device were required to be enrolled, more than half the aneurysms treated (473/896, 52.8%) were small (<10 mm).^{85,93} Combined neurologic morbidity and mortality for small unruptured anterior circulation aneurysms was 3.5% (11/311) and 0.0% (0/24) for small unruptured posterior circulation aneurysms. When specifically evaluating small (<10 mm) aneurysms located in the ICA, the rate of neurologic morbidity in ruptured and unruptured aneurysms was 4.1% (12/291), neurologic mortality was 1.4% (4/291) and the combined rate of neurologic morbidity

PR-NV16099	Version C	Page 50 of 144	Medtronic
		. ugo oo o	

and mortality for unruptured aneurysms was 3.4% (9/268). The overall IntrePED study results show that intracranial aneurysms measuring less than 10 mm are treated frequently and are associated with low complication rates.

Although there is some debate within the medical community regarding treatment of small and medium sized wide-neck aneurysms, it is clear from the literature that physicians worldwide treat a significant number small and medium aneurysms, both unruptured and ruptured. When deciding treatment approach, physicians take numerous factors into account in addition to aneurysm size, including age, aneurysm morphology, location, medical history and co-morbidities, previous SAH, and individual subject characteristics. After consideration of these factors, many times physicians conclude that the benefit of endovascular treatment outweighs the risk and subsequently treat these aneurysms. These cases demonstrate the need for endovascular treatment in a selected subject population and further, that these subjects may benefit from treatment with the Pipeline[™] Vantage Device.

It is also important to note that subjects with unruptured or ruptured (>30 days since occurrence) small and medium aneurysms proposed for enrollment in the current trial are those who have already been identified by their physician as being appropriate for endovascular treatment of their aneurysm. Investigators and subjects will first make the collective determination regarding the appropriateness of endovascular treatment based on their clinical expertise and experience. This will be the same process and decision that physicians, in consultation with subjects are currently performing when determining whether to treat subjects with small and medium aneurysms using endovascular coils. Only after the decision has been made by the physician and subject to treat the aneurysm through endovascular means, will the potential for enrollment into the proposed study be considered.

The following inclusion criterion will be used as a treatment inclusion risk mitigation measure to ensure only those small aneurysm subjects who demonstrate an appropriate level of aneurysm rupture risk, will be enrolled into this study. "Subject has been already selected for endovascular treatment of the target aneurysm. If the target aneurysm measures ≤5mm, risk factors leading to the determination to treat the aneurysm must be identified."

Internal Carotid Artery (up to the terminus)

Treatment with the PipelineTM Flex Embolization Device is currently indicated in the U.S. for the endovascular treatment of adults (22 years of age or older) with large or giant wide-necked intracranial aneurysms (IAs) in the internal carotid artery from the petrous to the superior hypophyseal segments. The PipelineTM Flex embolization device is also indicated for use in the internal carotid artery up to the terminus for the endovascular treatment of adults (22 years of age or older) with small and medium widenecked (neck width \geq 4 mm or dome-to-neck ratio < 2) saccular or fusiform intracranial aneurysm (IAs) arising from a parent vessel with a diameter \geq 2.0 mm and \leq 5.0 mm. The proposed study aims to include intracranial aneurysms in the ICA up to the terminus. The majority of aneurysms in the IntrePED study

PR-NV16099

Version C

Page 51 of 144

Medtronic

were located in the ICA (684/906, 75.5%) and ranged in size from small to giant (360 small, 272 large and 45 giant aneurysms, respectively).^{85,93} The combined neurologic morbidity and mortality rate for subjects with unruptured ICA aneurysms <10mm was 3.4% (9/268) and the combined neurologic morbidity and mortality rate for subjects with unruptured ICA aneurysms ≥10mm was 9.5% (27/285). These rates demonstrate that the Pipeline[™] Vantage Device can serve as a potentially safe treatment option for aneurysms of all sizes in the ICA (up to the terminus). Within this current study, the Pipeline[™] Vantage Device for the treatment of unruptured or ruptured (>30 days since occurrence), wide-necked intracranial aneurysms located in the ICA (up to the terminus) will be investigated.

Single- Arm Study Design

The proposed study design is a single-arm trial. As with the evaluation of the Pipeline[™] Embolization Device in the PUFs IDE study, a randomized controlled trial is not feasible for the evaluation of the Pipeline[™] Vantage Device due to the lack of an appropriate control treatment for small/medium and large/giant wide-neck intracranial aneurysms.

The target intracranial aneurysm population is likely to include many aneurysms that can be treated by Pipeline[™] Vantage Device but not by any particular single alternative treatment. In the U.S., wide-neck aneurysms are most commonly treated with stent-assisted coiling. Although intracranial stents are available, they are currently approved through a Humanitarian Device Exemption (HDE) and as such have only been proven to demonstrate safety and not effectiveness. Even the recent PMA approved stent, LVIS and LVIS Jr. showed relatively lower effectiveness outcomes with large/giant aneurysms (compared to small/medium aneurysms in the same study) (PMA 170013). As a result, stent-assisted coiling is not a feasible option for the control treatment. The use of coil embolization alone, is predicted to be infeasible in many subjects due to the wide-neck nature of the target aneurysms.

As a result, the study design for the evaluation of the Pipeline[™] Vantage Device is a prospective singlearm trial.

Conclusion

In summary, intracranial aneurysms can potentially rupture and lead to serious complications with significantly poor outcomes. SAH resulting from aneurysmal rupture is associated with a high mortality rate of greater than 40%.^{1,10} In addition to large and giant aneurysms, which have rupture rates of 18.4% and 50%, small and medium aneurysms warrant consideration for treatment.⁹⁹ The average size of ruptured intracranial aneurysms is approximately 6.6-6.8 mm. Small and medium wide-necked intracranial aneurysms are most commonly treated endovascularly with SAC, however, treatment outcomes are sub-optimal. Given the high long-term recanalization and retreatment rates reported with SAC, alternative options with sustained curative effects are necessary. Treatment with the Pipeline[™] Embolization Device has demonstrated high rates of long-term complete occlusion, low rates of retreatment and low rates of adverse transient and persistent neurologic events in large and giant wide-

ADVANCE Clinica	al Investigation Plan		
PR-NV16099	Version C	Page 52 of 144	Medtronic

necked intracranial aneurysms.^{54,55,85,93,127} Data collected in the IntrePED retrospective study and published literature suggests that the Pipeline[™] Embolization Device could also be a possible treatment option for small and medium wide-necked intracranial aneurysms.^{85,93}

Thus, the aim of the present study is to assess the Pipeline[™] Vantage Device beyond the present indication to include wide-neck intracranial aneurysms of all sizes in the ICA (up to the terminus).

PR-NV16099

[figure not shown]
7. Product Description

